1.1 Current Therapeutic Management of Pericarditis

There are no approved therapies for the treatment of recurrent pericarditis. Current treatments include nonspecific inhibitors of inflammation, i.e., aspirin, nonsteroidal anti-inflammatory drugs (NSAIDs), colchicine, and CS (Lilly et al 2013).

Aspirin and other NSAIDs are the first-line approach. Because high doses of aspirin and NSAIDs are often required, consideration must be given to gastric protection therapy, as potential risks of therapy include stomach ulcers and gastrointestinal (GI) bleeding, as well as renal and cardiovascular toxicity. Colchicine is another mainstay therapy for pericarditis and is commonly used with NSAIDs to hasten the response to NSAIDs and reduce the risk of subsequent recurrences. However, its use may be associated with the risk of fatal overdosing, significant drug interactions, and neuromuscular toxicity. In addition, approximately 10% to 15% of patients experience significant GI side effects with colchicine, including GI intolerance or severe diarrhea, requiring treatment discontinuation (Imazio et al 2016).

Available ESC guidelines stipulate that CS should be prescribed for the management of pericarditis episodes only in cases of incomplete response, intolerance, or contraindications to NSAIDs and colchicine because of their unfavorable long-term benefit-risk profile. Corticosteroid use is associated with side effects, including weight gain, diabetes, osteoporosis, avascular bone necrosis, and increased risk for infections (Imazio et al 2008). For the management of pericarditis, CS are usually administered at low to moderate doses and can provide rapid control of symptoms. However, they often require many months of tapering after the normalization of CRP levels. In addition, there is a high rate of pericarditis relapse when CS use is tapered or stopped (Lotrionte et al 2010; Imazio et al 2005; Maisch et al 2004), particularly in the absence of concurrent colchicine treatment.

Patients with recurrent pericarditis who are refractory or intolerant to current therapeutic management options or who require long-term administration of CS to control their disease can be particularly challenging to manage. As a last resort, some refractory patients are being referred to the surgical procedure of pericardiectomy, with variable outcomes. Multiple immunosuppressive medications have been used without consistent benefit (Baskar et al 2016).

1.2 Pathogenesis of Recurrent Pericarditis: Role of IL-1

Interleukin-1 is a key cytokine that drives the pathophysiology of many inflammatory processes, and it is implicated as a causative factor in various inflammatory diseases in humans.

[figure not shown]
The two distinct IL-1 genes, *IL1A* and *IL1B*, encode IL-1 α and IL-1 β , respectively. IL-1 α and IL-1 β bind to the universally-expressed cell surface receptor, IL-1 receptor type-1, triggering a cascade of inflammatory mediators. The precursor form of IL-1 α is expressed in keratinocytes, mucous membrane epithelial cells, and organs such as the liver and vascular endothelium in healthy individuals. During pathological states, IL-1 α moves to the cell surface or is released after cell death to activate IL-1 receptors in adjacent cells, thus beginning the cascade of sterile inflammation. IL-1 β ,

however, is not expressed in healthy individuals until a stimulus, such as microbial products or other chemokines, triggers its transcription in monocytes, tissue macrophages, and dendritic cells via the inflammasome. IL-1 drives the inflammatory cascade in classic autoinflammatory conditions, such as tumor necrosis factor (TNF)-associated periodic syndrome (TRAPS) and familial Mediterranean fever (FMF) and plays a significant role in systemic onset of juvenile idiopathic arthritis and in autoimmune diseases such as rheumatoid arthritis (Baskar et al 2016).

IL-1–blocking therapies are effective at controlling end-organ disease and damage in patients with various autoinflammatory disorders, and different strategies to block IL-1 have been used in clinical trials and demonstrated substantial success in controlling episodes of fever and elevations in acute-phase reactants (Cantarini et al 2015).

This mechanistic plausibility of IL-1 antagonism in addressing pathophysiology related to the inflammasome extends to other conditions characterized by sterile acute inflammation, such as recurrent pericarditis.

[figure not shown]

1.3 Rilonacept (KPL-914)

Rilonacept (designated in Kiniksa Pharmaceutical's development program as KPL-914) was developed by Regeneron Pharmaceuticals, Inc. (Regeneron) of Tarrytown, NY, and is approved with the trade name ARCALYST[®] in the US for the treatment of CAPS, including Familial Cold Auto-Inflammatory Syndrome (FCAS) and Muckle-Wells Syndrome (MWS) in adults and children age 12 and older. Rilonacept is currently manufactured and marketed as ARCALYST[®] by Regeneron. Rilonacept received marketing authorization in the European Union for the treatment of CAPS with severe symptoms, including FCAS and MWS in adults and children aged 12 years and older, but based on a request from Regeneron, the marketing authorization was withdrawn. The withdrawal was a business decision and was not related to any concern with the safety or efficacy of rilonacept.

Rilonacept is a recombinant fusion protein consisting of human cytokine receptor extracellular domains and the Fc portion of human IgG1. Rilonacept is a dimeric glycoprotein with a total molecular weight of approximately 250 kDa. The dimer is covalently linked by disulfide bonds in the Fc region. Rilonacept incorporates in a single molecule the extracellular domains of both receptors required for IL-1 signaling: the IL-1 type I receptor (IL-1R1) and the IL-1 receptor accessory protein (IL-1R-AcP) (Figure 1).

Rilonacept is expressed in recombinant Chinese hamster ovary (CHO) cells. Rilonacept blocks IL-1 by acting as a soluble decoy receptor that binds IL-1 and prevents its interaction with cell surface receptors.

Figure 1: Schematic of Rilonacept (KPL-914)

1.3.1 Safety of Rilonacept

For a detailed review of the available rilonacept safety data, please refer to the current Investigator Brochure and the ARCALYST® package insert (Section 13.1: ARCALYST® Prescribing Information). The available rilonacept safety data is summarized below.

Rilonacept has been evaluated in 23 studies, including 22 complete and 1 ongoing. In the completed studies, 2243 subjects (2152 patients and 91 healthy volunteers) were exposed to rilonacept. Thirty of these patients were pediatric (<18 years of age).

Doses up to 320 mg subcutaneously (SC) once weekly and 2000 mg intravenously (IV) monthly have been studied for different indications, including CAPS, gout, and other inflammatory disorders.

Injection Site Reactions

In clinical studies with rilonacept, the most common and consistently reported AE associated with rilonacept was injection site reaction (ISR). The ISRs included erythema, swelling, pruritus, mass, bruising, inflammation, pain, edema, dermatitis, discomfort, urticaria, vesicles, warmth, and hemorrhage. Most ISRs were mild to moderate. In the gout clinical studies, approximately 1% of subjects treated with rilonacept discontinued due to ISRs. Similar results have been seen in other patient populations.

Infections

Interleukin-1 blockade may interfere with immune response to infections. Serious life-threatening infections have been reported in clinical trials in subjects treated with rilonacept.

Changes in Laboratory Parameters

Cholesterol and lipid levels may be reduced in patients with chronic inflammation. Subjects treated with rilonacept in clinical trials experienced increases in their mean total cholesterol, high-density lipoprotein (HDL) cholesterol, low-density lipoprotein (LDL) cholesterol, and triglycerides.

Immunogenicity

As with all therapeutic proteins, there is a potential for immunogenicity. Antibodies directed against the receptor domains of rilonacept were detected using an enzyme-linked immunosorbent assay (ELISA). In clinical trials with rilonacept, approximately 30% to 35% of subjects tested positive for treatment-emergent antibodies to rilonacept on at least 1 occasion.

Systemic Hypersensitivity Reactions

Hypersensitivity reactions are a potential risk with protein therapeutics in general. In clinical studies with rilonacept, systemic hypersensitivity reactions have been rare.

Malignancies

The impact of treatment with rilonacept on the development of malignancies is not known. However, treatment with immunosuppressants, including rilonacept, may result in an increase in the risk for malignancies.

Fetal Defects

There are no adequate and well-controlled studies of rilonacept in pregnant women. Based on animal data, rilonacept may cause fetal harm. An embryo-fetal developmental toxicity study was performed in cynomolgus monkeys treated with 0, 5, 15, or 30 mg/kg given twice a week (highest dose is approximately 3.7-fold higher than the human dose of 160 mg based on body surface area). The fetus of the only monkey with exposure to rilonacept during the later period of gestation showed multiple fusion and absence of the ribs and thoracic vertebral bodies and arches. Exposure to rilonacept during this time period was below that expected clinically. Likewise, in the cynomolgus monkey, all doses of rilonacept reduced serum levels of estradiol up to 64% compared to controls and increased the incidence of lumbar ribs compared to both control animals and historical control incidences. In perinatal and postnatal developmental toxicology studies in the mouse model using a murine analog of rilonacept (0, 20, 100, or 200 mg/kg), there was a 3-fold increase in the number of stillbirths in dams treated with 200 mg/kg 3 times per week (the highest dose is approximately 6-fold higher than the 160 mg maintenance dose based on body surface area).

Nonteratogenic effects: A peri- and postnatal reproductive toxicology study was performed in which mice were administered a murine analog of rilonacept at doses of 20, 100, and 200 mg/kg SC 3 times per week (the highest dose is approximately 6-fold higher than the 160 mg maintenance dose based on body surface area). Results indicated an increased incidence in unscheduled deaths of the F1 offspring during maturation at all doses tested.

1.3.2 KPL-914-C001 Study with Rilonacept (KPL-914) in Recurrent Pericarditis

KPL-914-C001 is an open-label, single active-arm Phase 2 proof-of-concept study in subjects age ≥ 6 to 75 years old with recurrent idiopathic or post-pericardiotomy syndrome (PPS) pericarditis. The study includes a 6-week Treatment Period in which all the subjects receive once-weekly rilonacept 160 mg SC (2.2 mg/kg for subjects ≥ 6 and < 18 years old) following a loading dose of 320 mg SC in subjects ≥ 18 years old (4.4 mg/kg in subjects ≥ 6 and < 18 years old) in addition to background pericarditis therapies (NSAIDS, colchicine, CS). After completing the 6-week Treatment Period and based on response status, the subjects have the option to enter the 18-week Extension Period during which they continue to receive rilonacept at the same dose, but during which investigators are encouraged to wean and stop background pericarditis medications.

The primary objectives of the study are to explore clinical and biochemical endpoints of recurrent pericarditis symptomatology, as well as to assess feasibility to wean from concomitant pericarditis medication in the Extension Period while continuing treatment with rilonacept. The study population includes the following 5 subject categories (Parts):

- Part 1 enrolls symptomatic subjects with recurrent idiopathic pericarditis with an elevated marker of systemic inflammation (CRP level > 1 mg/dL).
- Part 2 enrolls symptomatic subjects with recurrent idiopathic pericarditis with CRP level ≤ 1 mg/dL that, in the opinion of the investigator, can be attributed to concomitant medications (e.g., CS) and with pericardial inflammation present on cardiac MRI confirmed by the imaging core lab.
- Part 3 enrolls subjects with CS-dependent recurrent idiopathic pericarditis not experiencing symptoms that would meet the diagnostic criteria for a recurrence of pericarditis.
- Part 4 enrolls symptomatic subjects with recurrent PPS with an elevated marker of systemic inflammation (CRP level > 1 mg/dL).
- Part 5 enrolls subjects with CS-dependent recurrent PPS not experiencing symptoms that would meet the diagnostic criteria for a recurrence of pericarditis.

Preliminary data in this ongoing study suggest that subjects enrolled in Part 1 experience improvements in pain, CRP levels, and other pericarditis parameters compared to baseline.

Adverse events observed in the study are consistent with the overall rilonacept safety profile.

2 Study Objectives and Endpoints

2.1 Primary Objective

The primary objective of this study is to assess the efficacy of rilonacept treatment in subjects with recurrent pericarditis.

2.2 Secondary Objective

The secondary objective of this study is to assess the safety of rilonacept treatment in subjects with recurrent pericarditis.

3 Investigational Plan

3.1 Study Design

This is a Phase 3, multi-center, double-blind, placebo-controlled, randomized withdrawal study with open-label extension, to assess the efficacy and safety of rilonacept treatment in subjects with recurrent pericarditis. This study has 5 periods ([Figure 2](#)).

3.1.1 Screening Period (up to 4 weeks)

During the screening period, assessment of disease characteristics, baseline therapy, and the pre-treatment workup will be completed during a period of up to 4 weeks.

3.1.2 Single-blind Run-In (RI) Period (12 weeks)

During the single-blind RI period, treatment with blinded rilonacept is administered and subjects are weaned off background standard of care (SOC) therapy for their pericarditis disease. Subjects will be blinded regarding the time of transition from the single-blind to the double-blind period; i.e., they will not be aware of the duration of the RI period.

In the single-blind RI period, subjects ≥ 18 years old will receive blinded rilonacept as an initial loading dose of 320 mg (2 SC injections of 160 mg each) at the RI baseline visit (2×2 ml), followed by a 160 mg (2 ml) SC dose once weekly throughout the RI period. Pediatric subjects (≥ 12 and < 18 years old) will receive an initial loading dose of blinded rilonacept 4.4 mg/kg (2 SC injections of 2.2 mg/kg each) at the RI baseline visit (maximum 2×2 ml), and then 2.2 mg/kg (maximum 2 ml) SC once weekly throughout the RI period.

The RI period includes:

- 1-week Stabilization period, during which blinded rilonacept is administered in addition to SOC pericarditis therapy, and the ongoing pericarditis episode is treated.
- 9-week Weaning period, during which subjects are weaned off background SOC pericarditis therapy, as applicable, while treatment with blinded rilonacept continues. The dosages of CS, NSAIDs, and colchicine will be tapered according to the weaning protocol in the Pharmacy Manual (for the purpose of the protocol, aspirin is considered an NSAID). In general, CS doses will be tapered off starting at RI Week 1 and will be withdrawn by RI Week 10 (over a total of 9 weeks). NSAID and colchicine doses will be tapered off starting at RI Week 4 and will be withdrawn by RI Week 10 (over a total of 6 weeks).
- 2-week Monotherapy period: Subjects who have been successfully weaned off background SOC pericarditis therapy will continue to receive blinded rilonacept.

Subjects who stopped background pericarditis medications and achieve Clinical Response on rilonacept monotherapy at RI Week 12/RW baseline will proceed into the double-blind placebo-controlled Randomized-Withdrawal (RW) period of the study. For definition of Clinical Response, refer to [Section 6.2.2](#).

Subjects who are unable to achieve Clinical Response on rilonacept monotherapy at RI Week 12/RW baseline are to be discontinued from study drug, transitioned to SOC pericarditis therapy at the investigator's discretion, and followed through the end of the RW period.

3.1.3 Double-blind Placebo-controlled RW Period (pericarditis recurrence event-driven duration with a minimum of 24 weeks)

During the RW period, subjects who were able to stop background pericarditis medications and who achieve Clinical Response on rilonacept monotherapy at RI Week 12/RW baseline will be randomized 1:1 to double-blinded administration of study drug:

- Rilonacept 160 mg (or 2.2 mg/kg in pediatric subjects ≥ 12 and < 18 years old) SC injections once weekly OR
- Matching placebo SC injections once weekly

Pericarditis Recurrence in the RW Period

For the definition of pericarditis recurrence, refer to [Section 6.2.3](#).

Upon pericarditis recurrence, subjects who report at least 1 day with pericarditis pain measurement ≥ 4 on the 11-point Numerical Rating Scale [NRS] and have 1 CRP value ≥ 1 mg/dL (either on the same day or separated by no more than 7 days) will receive bailout rilonacept (2 open-label injections of 160 mg rilonacept [or 4.4 mg/kg for pediatric subjects]) irrespective of randomized treatment assignment and as soon as at least 5 days have passed since the last study drug injection. The subjects transitioning to bailout rilonacept will remain blinded to their prior RW period treatment assignment. Sequential Oral Rescue Therapy (ORT), i.e., analgesics first, then NSAIDs, and then colchicine, can be added, if needed, at the discretion of the investigator, as outlined in [Section 5.8.3](#) and detailed in the Pharmacy Manual.

Subjects with pericarditis recurrence who do not meet the protocol criteria for bailout rilonacept will continue blinded study drug until they meet the protocol criteria for bailout rilonacept or through the end of the RW period. For those subjects, sequential ORT can be added to blinded study drug at the discretion of the investigator, as outlined in [Section 5.8.3](#) and detailed in the Pharmacy Manual.

All suspected pericarditis recurrence events in the RW period will be formally adjudicated by the Clinical Endpoint Committee (CEC), and only events that are confirmed by the CEC as pericarditis recurrences will be used in the Primary Endpoint analysis.

The RW period will continue until the prespecified number of primary endpoint (CEC-confirmed pericarditis recurrence) events have occurred and approximately 50 randomized subjects have

achieved a minimum of 24 weeks of treatment in the RW period. Based on projected event accrual and subject randomization, Kiniksa Pharmaceutical will determine the end of the RW period and announce to sites so that subject End of Randomized Withdrawal (EORW) visits can occur. All subjects, including those who have transitioned to open-label rilonacept or who prematurely discontinued study drug, should complete an EORW visit.

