- Change over time in SF-36 Mental Component Score
- Change in EQ-5D-5L
- Change over time in subject's sleep quality assessed with the ISI
- Change over time in ISI categories
- Number (percentage) of subjects who receive sequential ORT therapy for pericarditis recurrence (analgesics, NSAIDs, and/or colchicine) in the RW period

Efficacy endpoints for the RI period include:

- Proportion of subjects who achieved Clinical Response at the RI Week 12 visit
- Time to CRP normalization
- Number (percentage) of subjects with normalization of CRP at RI Week 12
- Change from baseline in pericarditis pain at RI Week 12
- Change from baseline in CRP level at RI Week 12
- Resolution of echocardiographic and ECG abnormalities (yes/no) at RI Week 12
- Percentage of days with no or minimal pain
- Proportion of subjects with absent or minimal pericarditis symptoms based on the PGIPS
- Proportion of subjects with absent or minimal pericarditis activity based on the PGA-PA
- Change over time in SF-36 Physical Component Score
- Change over time in SF-36 Mental Component Score
- Change in EQ-5D-5L
- Change over time in subject's sleep quality assessed with the ISI
- Change over time in ISI categories
- Number (percentage) of subjects who were off background SOC pericarditis therapy at RI Week 12

Efficacy endpoints for the LTE-TP include:

- Number (percentage) of subjects with pericarditis recurrences
- Proportion of subjects with Clinical Response
- Change over time in CRP levels
- Change over time in subject's assessments of pericarditis pain
- Percentage of days with no or minimal pain
- Proportion of subjects with absent or minimal pericarditis symptoms based on PGIPS
- Proportion of subjects with absent or minimal pericarditis activity based on PGA-PA

Statistical Methods Continued:

- Change over time in SF-36 Physical Component Score
- Change over time in SF-36 Mental Component Score
- Change in EQ-5D-5L
- Change over time in subject's sleep quality assessed with the ISI
- Change over time in ISI categories
- Number (percentage) of subjects requiring addition of SOC pericarditis therapy

Primary analysis of this study will be done after the 22nd CEC-confirmed pericarditis recurrence and after all subjects in the RW period have been treated for 24 weeks. Subjects who have not had an adjudicated pericarditis recurrence will be censored on the day of the last available assessment before data cutoff.

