3.1.5 Long Term Extension Follow-Up Period (LTE-FUP) (24 weeks)

All subjects in the LTE-TP will be followed in the LTE-FUP for an additional 24 weeks for safety and for potential pericarditis recurrence assessments.

The total duration of the study will be determined by the rate of enrollment, the rate of first recurrence of pericarditis events during the RW period, and the minimum duration of follow-up in the RW of 24 weeks. It is anticipated that study completers (including LTE-TP) will be dosed with rilonacept for approximately 1.2 years and up to 3 years based on enrollment assumptions and pericarditis recurrence events accrual time.

Figure 2: Overview of KPL-914-C002 Trial Design

Abbreviations: CS=corticosteroid; EOS=end of study, LTE=Long Term Extension; NSAID=nonsteroidal anti-inflammatory drug; RI=run in, RW=randomized withdrawal, SC=subcutaneously, TP=treatment period

a. The first dose given is a loading dose of rilonacept. In adult subjects ≥18 years old, 320 mg is given as 2 SC doses of 160 mg. In pediatric subjects ≥12 and <18 years old, 4.4 mg/kg is given as 2 SC doses of 2.2 mg/kg. After the loading dose, rilonacept will be administered as a 160 mg (adults) or 2.2 mg/kg (pediatric subjects) SC dose once weekly.

b. Subject's treatment duration will depend on when the subject is enrolled relative to the end of RW.

c. The adult dose is 160 mg SC once weekly. The pediatric dose is 2.2 mg/kg SC once weekly.

Note: This picture is not drawn to scale.

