7.4 Sample Size Calculations

For the purpose of sample size estimation, time to pericarditis recurrence is assumed to follow an exponential distribution. An event of interest is defined as a subject's first adjudicated recurrence of pericarditis. The following assumptions are used in the sample size calculation using EAST 6.4.1:

- | | |
|--|-------|
| • 1-sided significance level | 2.5% |
| • Power | 90% |
| • Median time to event (in weeks) in placebo | 8 |
| • Hazard ratio (rilonacept/placebo) | 0.244 |
| • Percentage of subjects in the RI period that will not reach RW | 10% |

Given these assumptions, a total of 22 adjudicated pericarditis recurrence events is required to achieve the power. About 25 subjects per arm (a total of 50 subjects) will be randomized. Considering 10% of subjects in the RI period that will not reach the RW period, approximately 56 subjects will be enrolled in this study.

Patient enrollment and the pericarditis recurrence event accrual will be closely monitored during the study. The monitoring activities will be done in a blinded fashion during the RW period. If the number of patients randomized is less than 50 and/or the time anticipated for the number of events required for the analysis of primary efficacy endpoint significantly exceeds the projected timeline, additional patients may be enrolled and/or randomized at Kiniksa Pharmaceutical's discretion. However, at this time it is anticipated that no more than 75 subjects will be enrolled into this study. Since the data cutoff will be the event date of the 22nd adjudicated pericarditis recurrence AND all subjects still in the RW period have been treated for 24 weeks, the actual power could be higher if the assumed hazard ratio holds.

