7.7.4 Analysis of Primary Efficacy Endpoint

Primary analysis of this study will be done after 22nd CEC-confirmed pericarditis recurrence AND after all subjects in the RW period have been treated for 24 weeks. The log rank test will be the primary method for the analysis of time to recurrence, stratified by the stratification variables for randomization.

A sensitivity analysis will be performed based on the investigator's judgement of pericarditis recurrence. Additional sensitivity may be defined in the SAP.

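### Section 3.1.3 and Section 7 give different rules for ending the randomized-withdrawal period; they agree only if about 50 subjects are randomized, and beyond that late-randomized subjects could be stopped before Week 24

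*Protocol*

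**What the plan says.** References are to version 1.1 of the protocol; version 1.0 has the same end rules.

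**The operational rule.** Section 3.1.3 states: "The RW period will continue until the prespecified number of primary endpoint (CEC-confirmed pericarditis recurrence) events have occurred and approximately 50 randomized subjects have". The rest of that sentence asks 24 weeks or more on RW treatment of those subjects. The section then has the sponsor determine the end of the period from projected events and randomization, and announce it to sites. The date is common to everyone. Footnote u of Table 1–2 schedules the final RW visit for all subjects once the date is announced, and Section 5.9 unblinds all sites and subjects at the end of the period.

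**The analysis rule.** Section 7.7.4 places the primary analysis after the 22nd confirmed recurrence "AND after all subjects in the RW period have been treated for 24 weeks". The synopsis says the same: "after all subjects in the RW period have been treated for 24 weeks". Section 7.4 defines the data cutoff by the 22nd event and the condition that "all subjects still in the RW period have been treated for 24 weeks".

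**Other statements of the minimum.** The heading of Section 3.1.3 gives the RW period a minimum of 24 weeks, and Section 3.1.5 refers to "the minimum duration of follow-up in the RW of 24 weeks".

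**How many may be randomized.** Section 7.4 plans: "About 25 subjects per arm (a total of 50 subjects) will be randomized". Section 4.1 words this as at least 50. Section 7.4 lets the sponsor add subjects if fewer than 50 are randomized or if events are late, and says: "However, at this time it is anticipated that no more than 75 subjects will be enrolled into this study".

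**The concern.** Section 3.1.3 is the text from which the end date will be announced, and its 24-week requirement covers only about 50 subjects. Section 7 covers all of them. Nothing says which governs, and no provision lets a late-randomized subject continue blinded to Week 24 after the announced date.

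What is at stake is the set of major secondary endpoints in Section 7.2.1. Maintained Clinical Response and the patient global impression are measured at Week 24. The percentage of days with no or minimal pain covers the first 24 weeks. Section 7.7.3 tests Clinical Response first and uses it as the gate to the other two. A subject brought to the closing visit at, say, RW Week 10 has no blinded Week 24 value and only a partial pain record. An analysis plan cannot recover data that the conduct rule stopped collecting.

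**Working it through.** **Inputs (Section 7.4 unless noted).** One-sided alpha 0.025; power 90%; hazard ratio 0.244; placebo median 8 weeks, exponential; 22 events; 1:1 allocation (Section 3.1.3); run-in loss 10%; enrollment ceiling 75. The protocol gives no accrual rate, so accrual below is an assumption: uniform over 26, 52 or 78 weeks.

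**1. The plan's own figures reproduce.**
- Events (Schoenfeld): 4 × (1.960 + 1.282)² / (ln 0.244)² = 21.12, rounded up to 22. Power with 22 events is 91.1%.
- Enrollment: 50 / 0.90 = 55.6, so 56.

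**2. Which condition in Section 3.1.3 sets the date?** With simultaneous entry of 50 subjects:
- Event probability by Week 24 on placebo: 1 − 2^(−24/8) = 0.875.
- On rilonacept: 1 − 2^(−0.244 × 24/8) = 0.398.
- Expected events: 25 × (0.875 + 0.398) = 31.8, well above 22. The expected count reaches 22 at about 12.2 weeks.

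With staggered entry, the two end dates were simulated as the later of the 22nd event and (a) the 50th randomization plus 24 weeks, or (b) the last randomization plus 24 weeks. For 56, 60 and 67 randomized and each accrual duration, the 22nd event came before the 50th subject's Week 24 in every simulated trial. At the planned rates the 24-week clause therefore sets the date.

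**3. Subjects exposed under Section 3.1.3**, reading approximately 50 as 50 and counting the first 50 randomized:

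| Randomized | Possibly short of Week 24 | Share |
|---|---|---|
| 50 | 0 | 0% |
| 56 (every planned enrollee randomized) | 6 | 11% |
| 60 | 10 | 17% |
| 67 (75 × 0.90 = 67.5) | 17 | 25% |

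Under the Section 7 rule the number is zero for any total, among subjects still in the period.

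**4. Sensitivity to slow events.** With 67 randomized and the hazard ratio held at 0.244, a placebo median of 24 weeks leaves the average number cut off at about 16 to 17. At a median of 52 weeks the event condition usually governs, and the average falls to roughly 1, 4 and 8 to 9 for accrual over 26, 52 and 78 weeks.

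**5. Extra time under the Section 7 rule.** With 67 randomized at the planned rates, the RW period ends later by about 6.5, 13 and 19.5 weeks for accrual over 26, 52 and 78 weeks.

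**The case against.** The strongest reply is that approximately 50 is simply the whole planned randomized population, so the two phrasings mean the same thing. The 24-week minimum is repeated in the heading of Section 3.1.3, the synopsis, Table 1–2 and Section 3.1.5. The projected minimum of about 1.2 years of dosing also fits 12 + 24 + 24 = 60 weeks, which presupposes a full 24 weeks in the RW period. And the sponsor sets the date, so it can follow the stricter text without breaching anything.

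This shows that the intention was probably 24 weeks for all. It does not settle which rule governs. The equivalence holds only when about 50 are randomized; Section 4.1 makes 50 a minimum and Section 7.4 allows additions. Discretion to follow the stricter rule is equally discretion to follow the looser one.

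The reply on size stands in large part. The 17 of 67 needs the enrollment ceiling together with the planned 10% run-in loss. If subjects are added because too few were randomized, the additions bring the total up towards 50. If they are added because events are slow, the event condition may itself hold the period open. Ordinary overshoot from 56 enrolled exposes at most 6.

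A reader might also infer four stronger things that the documents do not support:
- That Section 3.1.3 ignores events. It requires the prespecified number as well.
- That ending early would make the Section 7.7.4 condition impossible to meet. Section 7.4 limits it to subjects still in the RW period, and those past the closing visit no longer are.
- That everyone cut off moves to open-label drug. Section 3.1.4 makes this optional, subject to consent and the investigator's discretion.
- That the primary test is compromised. Subjects stopped early are censored, and the 22 events are still required.

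**Conclusion.** The protocol contains two end-of-period rules that diverge once more than about 50 subjects are randomized, which it allows. This is an inconsistency in the conduct rule, and it should be corrected before an end date is announced.

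The exposure is none at 50 randomized, up to 6 at 56, and at most about 17 of 67 (25%) at the ceiling. The 25% is an upper bound, not a forecast. It rests on the planned hazards, 10% run-in loss, approximately 50 read as exactly 50, and a sponsor that applies Section 3.1.3 literally. The harm would fall on the three major secondary endpoints as avoidable missing data. The primary comparison is little affected.

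**What to change.** In Section 3.1.3, keep the event condition and replace the clause about approximately 50 randomized subjects with: *and all randomized subjects still in the RW period have completed at least 24 weeks in the RW period*. Use the same sentence in the synopsis, Section 7.4 and Section 7.7.4. Stating time in the period rather than time treated also keeps the rule workable for subjects who stop study drug but remain in follow-up, as Section 4.2.2 provides.

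The cost is one harmonized sentence in four places. It needs no more subjects, and the required number of events stays at 22. If more than 50 are randomized, the period runs until 24 weeks after the last randomization, or longer if events lag. Section 7 already requires that wait.
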